## 2.8 Intracerebral Microdialysis for Performing a Pharmacodynamic Assessment by Measuring NSC-Mediated Conversion of 5-FU and 5-FC in the Brain

Microdialysis is a technique for continuously analyzing the concentration of a drug or biomolecule in the extracellular fluid (ECF) of body tissues, without significantly disturbing tissue function. This technique, first developed in the 1970s, consists of implanting into a body tissue a catheter that contains a semi-permeable membrane at its tip. The dialysis membrane acts as an artificial capillary, so that when perfusion fluid is slowly, continuously pumped through the microdialysis catheter, diffusion of molecules occurs down their concentration gradients as the ECF equilibrates with the perfusion fluid. The dialysate, i.e. solution that exits the probe, is then collected at regular intervals for analysis. The dialysate will contain a representative proportion of the molecule or drug that is in the ECF. The concentration of drug in the dialysate is not the true concentration in the tissue because full equilibration does not take place across the dialysis membrane when the flow of perfusion fluid is constant. However, the fraction of drug that is recovered in the dialysate is an indirect measurement of the free drug concentration in the interstitium.

Microdialysis has mainly been applied clinically to the study of head trauma (Goodman et al. 1999; Vespa et al., 2003, 2005, 2006) subarachnoid hemorrhage (Staub et al., 2000; Sarrafzadeh et al., 2002; Kett-White et al., 2003) and epilepsy (During et al., 1993; Lindberger et al., 2002; Scheyer et al., 1994). In these settings, intracerebral microdialysis catheters are used to monitor metabolic changes (for example, varying levels of lactate, glucose, and glutamic acid) in order to detect possible complications and to evaluate the effects of a therapeutic intervention. Intracerebral microdialysis is also a suitable method for measuring levels of chemotherapy in the brain (De Lange et al., 2000; Blakeley and Portnow, 2010) because microdialysis catheters can serially sample free drug concentrations in the peritumoral cerebral cortex or within the brain tumor itself (Bergenheim et al., 2005; Blakeley et al., 2009).

The Brain Tumor Program at City of Hope has developed expertise in performing intracerebral microdialysis. Having now placed microdialysis catheters in nearly 40 patients with brain tumors (Portnow et al., 2009, 2010, 2013a, 2013b), we have the largest experience in the United States with the applying this technique to perform neuropharmacokinetic and neuropharmacodynamic assessments of chemotherapy agents.

Unique and compelling data about new anticancer drugs can be obtained *in vivo* from patients with brain tumors using intracerebral microdialysis. Unlike studies in which the tumor is removed in order to measure intratumoral drug concentrations at one time point, intracerebral microdialysis can not only determine the time course of changes in drug concentrations in the brain; since tumor is left in place, it also allows observation of the clinical outcomes associated with the drug concentrations measured *in vivo*.

### 2.8.1 Intracerebral microdialysis catheters

The 70 Brain MD Catheter (M Dialysis, Solna, Sweden) has a semi-permeable membrane with a molecular weight cut-off of 20,000 daltons, and has received 510(k) clearance from the Food and Drug Administration as a Cerebral Tissue Monitoring System for adjunct use in monitoring brain trauma patients at risk for ischemia. This microdialysis catheter is smaller in caliber than the catheters that are typically used for performing ventriculostomies and monitoring intracranial pressure. With the use of image guidance, the catheter can be safely and accurately placed in brain interstitium. Stereotactic placement of intracerebral microdialysis catheters has been shown to be a safe procedure, with bleeding and infectious complication rates similar to those seen with stereotactic biopsy, craniotomy, and other types of intracerebral monitoring (Benjamin et al., 2004). In a study of intracerebral microdialysis catheter use in neurointensive care patients (Poca et al., 2006), 4 of 97 patients (3%) were found to have a small ( $\leq 1\text{mL}$ ) collection of blood around the catheter on follow-up CT scans. None of these bleeds were clinically significant, and no catheter-related infections were reported.

Each catheter has a gold tip that makes it visible on CT scan. Thus, confirmation of correct placement of the catheters can readily be obtained with a non-contrast CT scan of the brain. These catheters have safely

remained in patients for 1-2 weeks (Kett-White et al., 2003). Sample collections are done while patients are awake and mobile.

### 2.8.2 *In Vitro* Microdialysis Recovery Data for 5-FU and 5-FC

Prior to performing intracerebral microdialysis in study patients, *in vitro* studies were done to estimate the fractional recovery of 5-FU and 5-FC at a given flow rate. Slower perfusion rates produce a higher fractional recovery (i.e. a concentration of drug in the dialysate that is close to the true interstitial drug concentration), but a longer sample collection interval is needed. The *in vitro* assessments were performed with the same microdialysis equipment that will be used in this clinical trial. A 70 Brain MD Catheter was placed into a reservoir containing a solution with a known concentration 5-FU and 5-FC. The inlet tubing of the catheter was attached to a syringe containing artificial CSF, and the syringe was placed in a variable flow rate pump (107 MD Pump). Artificial CSF perfused through the microdialysis catheter at different flow rates (0.5 – 5  $\mu$ l/min) and serial samples of dialysate were collected. We also performed an experiment to determine how much 5-FU and 5-FC bind to the tubing of the microdialysis equipment. A solution of known concentrations of 5-FU and 5-FC perfused a 70 Brain MD Catheter, while it sat in a reservoir containing a solution of the same concentrations of 5-FU and 5-FC.

The City of Hope Analytical Pharmacology Core Facility (APCF) developed a quantitative assay for 5-FU and 5-FC, and the concentration of these drugs in the dialysate samples were determined by liquid chromatography/tandem mass spectrometry (LC/MS/MS). At a flow rate of 1  $\mu$ l/min, the fractional recoveries of 5-FC and 5-FU were  $92 \pm 2.1\%$  and  $91 \pm 1.5\%$ , respectively. Binding of either drug to the catheter tubing was negligible (< 5%).

## 2.9 Overview of Proposed Study

Based on the encouraging safety data from our first-in-human pilot feasibility study of 1 cycle of intracranially administered CD-expressing NSCs and oral 5-FC in patients with recurrent high-grade gliomas, we will now perform a phase I clinical trial to define the phase II recommended doses of CD-expressing NSCs given in combination with 5-FC and leucovorin and determine the feasibility of administering repeat cycles of study treatment in patients with recurrent high-grade gliomas. A standard “3 + 3” dose escalation schema will be used, and 4 dose levels of study treatment will be tested. The starting number of NSCs will be  $5 \times 10^7$ , which is a dose that was well-tolerated by patients in the first study. Due to volume limitations for intracerebral administration, the highest dose of NSCs to be tested will be  $1.5 \times 10^8$ . The 5-FC will not be dose-escalated, but leucovorin, which potentiates the efficacy of 5-FU, will be added after dose escalation of the NSCs is completed.

Initially, the NSCs will be injected intracranially on cycle 1, day 1 when study patients undergo tumor resection or biopsy. Afterwards, there will be a waiting period of 3 days to allow time for the NSCs to distribute among foci of tumor. Patients will then take a 7 day course of oral 5-FC (dose level 4 patients will also take leucovorin). Repeat doses of NSCs will be administered through a Rickham placed at the time of surgery. The length of a treatment cycle will be 28 days. NSCs will be given on days 1 and 15 followed by 5-FC and leucovorin (dose level 4 patients) on days 4-10 and 18-24. Brain MRIs will be performed at the end of every even cycle of study treatment to evaluate response.

Immunologic correlative studies will be performed to assess for the possible development of NSC immunogenicity after repeat exposure to the allogeneic NSCs, and we will measure conversion of 5-FC to 5-FU by the NSCs. Once the maximum tolerated dose (MTD) of the combination therapy is predicted, if the MTD is not met, the maximum feasible dose (MFD), patients in this cohort will undergo intracerebral microdialysis during the first part of cycle 1 to quantify NSC-mediated conversion of 5-FC to 5-FU at the MTD/MFD level.

## 3.0 Patient Eligibility

---

### 3.1 Inclusion Criteria

#### 3.1.1 Disease Status

- 3.1.1.1 Patient has had a prior, histologically-confirmed, diagnosis of a grade III or IV glioma (including glioblastoma, anaplastic astrocytoma, gliosarcoma, anaplastic oligodendrogloma, or anaplastic oligoastrocytoma), or has a prior, histologically-confirmed, diagnosis of a grade II glioma and now has radiographic findings consistent with a high-grade glioma (grade III or IV).
- 3.1.1.2 Imaging studies show evidence of recurrent, supratentorial tumor(s). The presence of infratentorial tumor is allowed as long as the patient also has supratentorial disease that is amenable to resection or biopsy.
- 3.1.1.3 Patient's high-grade glioma has recurred or progressed after prior treatment with brain radiation and temozolomide.

#### 3.1.2 Age Criteria, Performance Status and Life Expectancy

- 3.1.2.1 Patient must be at least 18 years old.
- 3.1.2.2 Patient has a Karnofsky Performance Status of  $\geq 70\%$ .
- 3.1.2.3 Patient has a life expectancy of  $\geq 3$  months.

#### 3.1.3 Child Bearing Potential

The effects of this treatment on a developing fetus are unknown. Therefore, female patients of childbearing potential and sexually-active male patients must agree to use an effective method of contraception while participating in this study. Women of childbearing potential must have a negative pregnancy test  $\leq 2$  weeks prior to registration.

#### 3.1.4 Protocol-Specific Criteria

- 3.1.4.1 The patient must be in need of a craniotomy for tumor resection or a stereotactic brain biopsy for the purpose of diagnosis or differentiating between tumor progression versus treatment-induced effects following radiation therapy  $\pm$  chemotherapy.
- 3.1.4.2 Based on the neurosurgeon's judgment, there is no anticipated physical connection between the post-resection tumor cavity and the cerebral ventricles.
- 3.1.4.3 Patient must have adequate bone marrow function (defined as an absolute neutrophil count (ANC) of  $\geq 1500$  cells/mm $^3$  and platelet count  $\geq 100,000$  cells/mm $^3$ , adequate liver function with total bilirubin  $\leq 2.0$  mg/dl and AST (SGOT)  $\leq 4$  times the institutional upper limit of normal, and a serum creatinine  $\leq$  the institutional upper limit of normal.

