#### 5.2.4 Cycle 1 Days 4-10: Administration of 5-FC (and leucovorin for dose level 4 patients)

If the patient has recovered well from any immediate post-operative effects, is tolerating oral intake, and requiring less than 16 mg/day of dexamethasone by day 4, then s/he will take oral 5-FC, 37.5 mg/kg every 6 hours (dose level 4 and expansion cohort patients will also take oral leucovorin, 25 mg every 6 hours) on days 4-10.

The patient will be discharged from the hospital when medically ready and may proceed with or finish taking the 7-day course of 5-FC (and leucovorin if on dose level 4) as an outpatient.

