## 5.6 Study Design

The study will implement a standard 3+3 design. The goal will be to determine the maximum tolerated dose (MTD), which is defined as the highest dose level tested in which fewer than 33% of patients experienced a DLT attributable to the treatment regimen of NSCs with 5-FC and leucovorin, when at least 6 patients were treated at that dose and are evaluable for toxicity. If the MTD has not been reached with 1.5 x 108 NSCs, 37.5 mg/kg q6h 5-FC and 25 mg q6h leucovorin (dose level 3 plus leucovorin), then that dose will be termed the maximum feasible dose (MFD).

- 5.6.1** Phase I cohorts will be of 3 or 6 participants, as indicated by the dose-escalation criteria.
- 5.6.2** The dose schedule is provided in the table in section 5.7. The first cohort of patients will start at dose level 1.
- 5.6.3** Dose escalation will proceed through the identified doses without skipping any dose levels.
- 5.6.4** *Enrollment of the first 3 patients to dose levels 1-3 will be staggered* by requiring that each of the first 3 patients be separately observed for 4 weeks (or until the DLT assessment period has ended) before the next patient can start treatment on that dose level.
- 5.6.5**
- 5.6.6** Dose escalation rules:
  - 5.6.6.1 If 0/3 study participants experiences a DLT, the next cohort of 3 study patients will be treated at the next higher dose level.
  - 5.6.6.2 If 1/3 study participants experiences a DLT, the cohort will be expanded by another 3 study participants who will be treated at the same dose level for a total of 6 study participants.
  - 5.6.6.3 If 1/6 participants experiences a DLT, the next cohort of 3 study participants will be treated at the next higher dose level.
  - 5.6.6.4 If 2 or more participants of either a 3 participant or 6 participant cohort encounter a DLT, then the MTD has been exceeded. If applicable, three (more) participants will be enrolled at the next lower dose level.
  - 5.6.6.5 At least 6 patients will be treated at the MTD (or MFD, if the MTD is not reached).

For a patient to be counted for dose escalation, s/he must receive at least 80% (+/- 5%) of the assigned NSCs on days 1 and 15 and 80% (+/- 5%) of the 5-FC (and leucovorin, as indicated) on days 4-10 and 18-24 during cycle 1 and be followed up to and including cycle 2 day 1 safety assessments or have experienced a DLT.

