### **6.3.3 Criteria for First Administration of 5-FC (and leucovorin)**

For Cycle 1 Day 4 5-FC (and leucovorin) administration to proceed, the participant must have recovered well from any immediate post-operative effects **and** requires no more than 16 mg/day of dexamethasone. Otherwise the participant will be removed from treatment. Criteria found in Section 6.3 (Dose modifications) also apply.

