### **6.3.4 Dose Modifications**

Table 6.3.4 details the criteria for disrupting treatment, dose modification and treatment discontinuation following an adverse event. See section 6.3.1 for general guidelines. The agent listed in Table 6.3.4 indicates the drug to which the toxicity is likely attributed based on previous trials of 5-FC (with leucovorin) and possible anticipated toxicities to the CD-NSCs.

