Renal Toxicity Use Cockcroft & Gault formula and actual body weight to determine calculated creatinine clearance		
Calculated creatinine clearance 21.0 ml/min – $< 51.0$ ml/min	5-FC	Increase 5-FC interval to Q12 hours; if leucovorin is being administered, increase leucovorin interval to Q12 hours.
Calculated creatinine clearance 10.0 ml/min – $< 21.0$ ml/min		Increase 5-FC interval to Q24 hours; if leucovorin is being administered, increase leucovorin interval to Q24 hours.
Calculated creatinine clearance $< 10.0$ ml/min		Increase 5-FC interval to Q48 hours; if leucovorin is being administered, increase leucovorin interval to Q48 hours.
Gastrointestinal		
Diarrhea Grade 1 (2-3 stools/day $>$ pretreatment)	5-FC (with leucovorin)	Maintain treatment
Diarrhea Grade 2 (4-6 stools/day $>$ pretreatment)		Hold both study drugs until resolved to $\leq$ grade 1, then resume treatment at pre-hold dose
Diarrhea Grade 3 (7-9 stools/day $>$ pretreatment) while on optimal anti-diarrhea therapy		Hold study treatment until the diarrhea decreases to $\leq$ grade 1
		
For patients not taking leucovorin Restart treatment with a 25% decrease in 5-FC from the pre-hold dose.
 
For patients taking leucovorin First event: resume treatment at the same dose of NSCs and 5-FC, but permanently discontinue leucovorin. Additional events: resume treatment with a 25% dose reduction of 5-FC from the pre-hold dose.

Diarrhea Grade 4 (≥10 stools/day > pretreatment) while on optimal anti-diarrhea therapy	5-FC (with leucovorin)	Hold study treatment until the diarrhea decreases to ≤ grade 1  For patients not taking leucovorin Restart treatment with a 25% decrease in 5-FC from the pre-hold dose.  For patients taking leucovorin First event: resume treatment at the same dose of NSCs and 5-FC, but permanently discontinue leucovorin. Additional events: resume treatment with a 25% dose reduction of 5-FC of the pre-hold dose.
Vomiting or Nausea Grade 1		Maintain treatment
Vomiting or Nausea Grade 2		Maintain treatment

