### 7.3 Definitions

**Adverse event (AE)** - An adverse event is any untoward medical experience or change of an existing condition that occurs during or after treatment, whether or not it is considered to be related to the protocol intervention.

**Unexpected Adverse Event [21 CFR 312.32 (a)]** – An adverse event is unexpected if it is not listed in the investigator's brochure and/or package insert; is not listed at the specificity or severity that has been observed; is not consistent with the risk information described in the protocol and/or consent; is not an expected natural progression of any underlying disease, disorder, condition, or predisposed risk factor of the research participant experiencing the adverse event.

**Expected Adverse Event** - Any event that does not meet the criteria for an unexpected event OR is an expected natural progression of any underlying disease, disorder, condition, or predisposed risk factor of the research participant experiencing the adverse event

**Serious Adverse Event (SAE) [21 CFR 312.32]** is defined as any expected or unexpected adverse event that results in any of the following outcomes:

- Death
- Is life-threatening event (places the subject at immediate risk of death from the event as it occurred);
- Requires in-patient hospitalization (not required as part of the treatment) or prolongation of existing hospitalization;
- A persistent or significant disability/incapacity;
- A congenital anomaly/birth defect
- Secondary Malignancy, or
- Any other adverse event that, based upon appropriate medical judgment, may jeopardize the subject's health and may require medical or surgical intervention to prevent one of the outcomes listed above (examples of such events include allergic bronchospasm requiring intensive treatment in the emergency room or at home, blood dyscrasias of convulsions that do not result in inpatient hospitalization, or the development of drug dependency or drug abuse).

**Unanticipated problem (UP)** – Any incident, experience or outcome that meets all three of the following criteria:

1. Unexpected (in term nature, severity, or frequency) given the following: a) the research procedures described in the protocol-related documents such as the IRB approved research protocol, informed consent document or Investigator Brochure (IB); and b) the characteristics of the subject population being studied; **AND**

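### Renal entry screen uses serum creatinine only, while Table 6.3.4 sets the 5-FC interval by Cockcroft-Gault clearance, so a few patients could be eligible with a baseline clearance already below the 51 ml/min cut-off

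*Combined protocol and SAP*

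**What the plan says.** **Entry.** Section 3.1.4.3 sets the renal limit in the same sentence as the liver limits: AST up to 4 "times the institutional upper limit of normal, and a serum creatinine" at or below the institutional upper limit of normal (ULN). Sections 3.1 and 3.2 contain no clearance criterion, no upper age limit and no lower weight limit. Section 3.3, the gate for going on to 5-FC, looks only at oral intake and dexamethasone dose.

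**Dosing.** The renal block of Table 6.3.4 uses a different measure: "Use Cockcroft & Gault formula and actual body weight to determine calculated creatinine clearance". At 21.0 to below 51.0 ml/min the instruction is "Increase 5-FC interval to Q12 hours; if leucovorin is being administered, increase leucovorin interval to Q12 hours".

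**First 5-FC dose.** Three places bear on it and do not fully agree.
- Section 6.3.3, on the cycle 1 day 4 dose, says "Criteria found in Section 6.3 (Dose modifications) also apply".
- Section 5.2.4 attaches no renal condition: a patient who has recovered, is eating and is on a low enough steroid dose, "then s/he will take oral 5-FC, 37.5 mg/kg every 6 hours".
- Section 6.3.4 describes the table as covering "dose modification and treatment discontinuation following an adverse event", and Section 7.3 defines the term: "An adverse event is any untoward medical experience or change of an existing condition that occurs during or after treatment".

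**Counting.** Section 5.6 states: "For a patient to be counted for dose escalation, s/he must receive at least 80" percent, with a 5-point tolerance, of the assigned NSCs and the same percentage of the 5-FC in cycle 1, unless there was a DLT. Patients who do not count are still followed for toxicity and are replaced. Section 13.1 allows for 3 replacements.

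**The concern.** The entry screen and the dosing table measure renal function differently. Creatinine takes no account of age, sex or weight; Cockcroft-Gault does. A patient can therefore pass entry while already in the band where the table extends the 5-FC interval.

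The documents do not settle what happens next. On one reading, the patient has brain surgery and an intracerebral cell dose, takes half the planned 5-FC doses and cannot inform the dose decision. On another, the patient takes every-6-hour dosing at a clearance where the table would lengthen the interval, although Section 8.2.4 says more than 90% of 5-FC is excreted unchanged by glomerular filtration.

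Either outcome could be foreseen. Screening chemistry is due within 14 days before surgery (Section 10.0, footnote 2), but no entry rule turns it into a clearance. The next scheduled chemistry is on day 3 (footnote 12), after the day 1 cells. A replaced patient uses part of the 3-patient allowance and, if among the first three at dose levels 1 to 3, adds another staggered 4-week wait (5.6.4).

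**Working it through.** **The plan's own figures first.** Section 13.1 gives two results for 6 patients at the MTD.
- Chance of seeing a toxicity with true rate 0.25: 1 − 0.75^6 = 0.822, matching the stated 82%.
- Largest half-width of the exact 90% interval, at 3 of 6: (0.847 − 0.153)/2 = 0.347, matching the stated 0.35.

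Both are conditional on 6 patients at the MTD, so replacing a patient changes neither.

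**Who can be eligible with clearance below 51 ml/min?** Clearance = (140 − age) × weight / (72 × creatinine), times 0.85 for women. The cut-off of 51 is from Table 6.3.4. The institutional ULN is not given; I assume 1.0 to 1.3 mg/dl. First whole age at which clearance is below 51:

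| Patient | Creatinine (mg/dl) | Age | Clearance (ml/min) |
|---|---|---|---|
| Woman, 50 kg | 1.0 | 54 | 50.76 |
| Woman, 60 kg | 1.0 | 69 | 50.29 |
| Woman, 60 kg | 1.1 | 61 | 50.87 |
| Woman, 60 kg | 1.2 | 54 | 50.76 |
| Woman, 70 kg | 1.0 | 79 | 50.41 |
| Woman, 70 kg | 1.1 | 73 | 50.33 |
| Woman, 70 kg | 1.2 | 66 | 50.96 |
| Man, 70 kg | 1.2 | 78 | 50.23 |
| Man, 70 kg | 1.3 | 72 | 50.85 |
| Man, 80 kg | 1.2 | 85 | 50.93 |
| Man, 80 kg | 1.3 | 81 | 50.43 |

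Example: 60 kg woman, 69 years, 1.0 mg/dl: 71 × 60 / 72 × 0.85 = 50.29. By contrast, a man of 55 years and 80 kg at 1.2 mg/dl has 85 × 80 / 86.4 = 78.7 and is unaffected.

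**Doses under a 12-hour interval.** Planned: 4 per day × 7 days × 2 courses = 56. Every 12 hours throughout: 2 × 7 × 2 = 28, and 28/56 = 50%. Against the 6-hourly schedule the floor is 0.80 × 56 = 44.8 doses, or 0.75 × 56 = 42 with the tolerance. Twenty-eight fails both.

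**Does the shortfall count as a DLT?** Criterion 1 in 5.5 covers receiving under 80% of treatment only when the cause is a toxicity related to a study agent. A low clearance present before treatment is not that. So, absent some other DLT, the patient is not counted.

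**A fall after entry.** A patient at 55 ml/min reaches 51 with a creatinine rise of 55/51 − 1 = 7.8%. A 60 kg woman aged 61 goes from 55.96 at 1.0 mg/dl to 50.87 at 1.1. If this is first seen on day 15, only the second course is every 12 hours: 28 + 14 = 42 of 56, or 75.0%. That is at the tolerance limit for the whole cycle, but 14/28 = 50% of that course.

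**How many replacements?** The share affected cannot be derived. If 5%, 10% or 20% of 18 enrolled patients were affected (assumed), the binomial chance of needing more than 3 replacements would be about 1%, 10% or 50%.

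**The case against.** The strongest reply is that replacement needs two unsettled readings to go the same way.

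1. Table 6.3.4 must apply to a baseline value. It is framed around adverse events, which 7.3 places during or after treatment, and 5.2.4 orders 6-hourly dosing with no renal condition. The principal investigator may also keep a dose in writing for a toxicity thought unlikely to be related (6.3.1.6).
2. The 6-hourly schedule must be the denominator. In 5.6 the word assigned is attached to the NSCs, not the 5-FC. If the renally adjusted schedule is the denominator, the patient has taken all of it and counts.

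Both points stand. The bare clearance thresholds and 6.3.3 support applying the table on day 4, but do not prove it. A reader might infer that an affected patient will certainly start on the longer interval and be replaced; the text does not establish that.

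A reader might also infer that half the doses means half the exposure and so a misplaced MTD. The documents do not support this: with more than 90% renal excretion, fewer doses at reduced clearance need not halve exposure.

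Nor are patients whose clearance falls after entry generally lost. Section 6.2.3.1 lists creatinine elevation and renal failure as expected 5-FC toxicities, and possible attribution is enough for a DLT. A related fall that leaves the patient below 80% of treatment can meet criterion 1, and a patient with a DLT is counted.

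Finally, interval extension is a reasonable way to treat reduced clearance, replacement is already budgeted, and one sentence in 5.6 could settle evaluability without excluding anyone. That limits the severity. But that sentence would not settle which schedule a patient with low baseline clearance should start on.

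**Conclusion.** The mismatch between the entry screen and the dosing table is real, and its consequence is conditional. If the table applies at the first dose and 5.6 uses the 6-hourly denominator, the patient takes 50% of cycle 1 doses and, absent a DLT, is replaced after surgery and cells. If the table waits for an adverse event, the patient takes full 6-hourly dosing at a clearance where the table would extend the interval. If the adjusted schedule is the denominator, the patient counts at half the planned dose frequency. The protocol states none of these as intended.

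The likely size is small. It arises mainly in lighter or older women with creatinine near an assumed ULN of 1.0 to 1.3 mg/dl, and the cases probably fit within the 3-patient allowance. No distortion of the MTD or of the 13.1 figures is shown. This is a low-severity point, worth acting on because the remedy is cheap and the cell dose cannot be undone.

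**What to change.** Add to 3.1.4.3, alongside the creatinine limit, a screening creatinine clearance of at least 51 ml/min by Cockcroft-Gault with actual body weight, as in Table 6.3.4. This costs one eligibility line and one calculation from screening chemistry, age, sex and the weight already needed for mg/kg dosing. The downside is that a few older or lighter patients, whom the table could manage by interval, are excluded from a small single-site trial. The floor also gives no margin against a small later fall.

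As a secondary clarification, state in 5.6 whether the 80% of 5-FC is measured against the 6-hourly or the renally adjusted schedule, and whether over the whole cycle or per course. Note there that a fall in clearance after entry that is at least possibly related to study agents and leaves the patient below 80% of treatment can be a DLT under criterion 1, and would then be counted. This costs a sentence or two.
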